## **8.2 Safety Monitoring**

Safety assessments will consist of monitoring and recording all adverse events and serious adverse events, the regular monitoring of hematology and blood chemistry parameters and regular physical examinations. Adverse events will be evaluated continuously throughout the study. Safety and tolerability will be assessed according to the NIH/NCI Common Terminology Criteria for Adverse Events version 4.0 (CTCAE v4.03) that is available at:

<http://evs.nci.nih.gov/ftp1/CTCAE/About.html>

The principal investigator will monitor the data and toxicities to identify trends and will be responsible for revising the protocol as needed to maintain safety. Serious adverse events will be reported to the IRB in accordance with IRB and Moffitt institutional policies and to the FDA as described below. The Protocol Monitoring Committee (PMC) at Moffitt monitors its assigned ongoing research protocols for: adverse event reporting, data and safety monitoring, and internal audit findings. The PMC, upon review of any agenda item, may approve the study for continuation, require revisions, suspend or close a protocol.

Investigators will provide to the PMC the following information for data and safety monitoring: statistical report of the study's progress, summary of adverse events and deviations. Safety and monitoring reports are to be submitted to the PMC after completing each odd numbered dose level (i.e., 1,3,5, etc), or more frequently if requested by the PMC. A final safety and monitoring report must be submitted to the PMC within three months of defining the maximum tolerated dose (MTD).

### **8.2.1 Internal Monitoring Plan**

The trial will be monitored per Moffitt Cancer Center policy MRI-P.PSO.03, *Monitoring of Investigator Initiated Clinical Research*. Data will be captured in Oncore, Moffitt's Clinical Trials Management System, Regulatory documents and case report forms will be monitored internally according to Moffitt Cancer Center Monitoring Policies. Monitoring will be performed regularly to verify data is accurate, complete and verifiable from source documents; and the conduct of the trial is in compliance with the currently approved protocol/amendments, Good Clinical Practice, and applicable regulatory requirements.

### **8.3 Reporting of Serious Adverse Events**

Moffitt Cancer Center will report SAEs within 24 hours of the study team becoming aware of the event by completing an SAE report in OnCore, the clinical trial management system.

The definition of serious adverse events (SAEs) is given in Section 8.1.1.

Each serious adverse event must be followed up until resolution or stabilization, by submission of updated reports to the designated person. An isolated laboratory abnormality that is assigned

grade 4, according to CTCAE definition, is not reportable as an SAE; unless the investigator assesses that the event meets standard ICH criteria for an SAE. CTCAE grade 4 baseline laboratory abnormalities that are part of the disease profile should not be reported as an SAE, specifically when they are allowed or not excluded by the protocol inclusion/exclusion criteria.

### **Reporting Serious Adverse Events (SAEs) to the FDA**

Any event that is both serious and unexpected must be reported to the FDA as soon as possible and, in no event, later than 7 days (death or life-threatening event) or 15 days (all other SAEs) after the investigator's or institution's initial receipt of the information. SAEs may be reportable to the FDA for both FDA-approved (post-market) drugs as well as investigational agents.

For an event to be reportable to the FDA, it must meet **both** of the following requirements as determined by the principal investigator of the study:

1. The event is possibly, probably or definitely **related** to the agent
2. The event is **unexpected** (i.e., not listed in the protocol, investigational brochure, or informed consent)

Expedited reporting to the FDA on a MedWatch 3500A form will be used for all unexpected and related serious adverse events as defined in 21 CFR 312.32.

The current MedWatch mandatory reporting form FDA 3500A can be found on the FDA website:

<http://www.fda.gov/Safety/MedWatch/HowToReport/DownloadForms/default.htm>

Use: [Form FDA 3500A - Mandatory Reporting](#)

Complete the **MedWatch** report and mail it to the appropriate address below (please also see **FDA reporting fax number** under section 7.4.2):

#### **To report an event for an INVESTIGATIONAL AGENT under investigational new drug applications:**

Send a narrative of the event with circumstances, IND number, and why it is related and unexpected to the H. Lee Moffitt Cancer Center Regulatory Affairs IND Office. A MedWatch report for the event would suffice. The Regulatory Affairs IND Office at Moffitt Cancer Center will submit the reportable event as an IND safety report to the FDA on behalf of the principal investigator.

If applicable, the site should also follow protocol guidelines for additional reporting to government agencies.

When required, and according to local law and regulations, serious adverse events must be reported to the Ethics Committee and Regulatory Authorities.

All serious adverse events should be reported to Merck and Janssen within 24 hours. In the event of such an event, the investigator should refer to the Pharmacovigilance section of the contract for reporting procedures. The completed Medwatch/case report should be faxed immediately upon completion to the below:

Merck Global Safety. (Attn: Worldwide Product Safety; [contact])  
Janssen Drug Safety: ([[contact]](mailto:[contact])) or by fax if email is unavailable [contact]).

**The Investigator may report serious adverse events (SAEs) as described below.**

A MedWatch form available at <http://www.fda.gov/medwatch/>

All reports shall be faxed to:

#### **8.4 Pregnancies**

Although pregnancy and lactation are not considered adverse events, it is the responsibility of investigators or their designees to report any pregnancy or lactation in a subject (spontaneously reported to them) that occurs during the trial.

Pregnancies and lactations that occur after the consent form is signed but before treatment allocation/randomization must be reported by the investigator if they cause the subject to be excluded from the trial, or are the result of a protocol-specified intervention, including but not limited to washout or discontinuation of usual therapy, diet, placebo treatment or a procedure.

Pregnancies and lactations that occur from the time of treatment allocation/randomization through 120 days following cessation of treatment, or 30 days following cessation of treatment if the subject initiates new anticancer therapy, whichever is earlier, must be reported by the investigator. All reported pregnancies must be followed to the completion/termination of the pregnancy. Pregnancy outcomes of spontaneous abortion, missed abortion, benign hydatidiform mole, blighted ovum, fetal death, intrauterine death, miscarriage and stillbirth must be reported as serious events (Important Medical Events). If the pregnancy continues to term, the outcome (health of infant) must also be reported.

Such events must be reported within 24 hours to the Principal Investigator. Within 24 hours of the Investigator becoming aware, the pregnancy must be reported to:

Merck Global Safety. (Attn: Worldwide Product Safety; [contact])  
Janssen Drug Safety: Janssen Secure Email ([[contact]](mailto:[contact])) or by fax if email is unavailable [contact]).

## **9. Statistical Methods and Data Analysis**

### 9.1 Definition of Study Endpoints

To meet the objectives for this study, data for the following endpoints will be collected:

- Safety and Tolerability (Phase I)
- Disease control rate (CR + PR+ SD) at 4 months (Phase II)
- Tumor response by RECIST 1.1 and irRC (Secondary)
- Exploratory biomarkers, including genetic sequencing and cytokine multiples assay (Exploratory)

### 9.2 Determination of sample size

The primary objective of the phase I portion of this study is to investigate the safety and tolerability and thereby identify the recommended dose of ibrutinib in combination with pembrolizumab for evaluation in future clinical studies. Hence the number of subjects has been based on the desire to obtain adequate tolerability, safety and pharmacodynamic data while exposing as few subjects as possible to the investigational product and procedures.

For the dose escalation phase of the study, cohorts of 3-6 evaluable subjects (who have either failed to respond or relapsed following standard treatment, were unable to tolerate, or were not eligible for standard treatment) will be required. The total number of subjects will depend upon the number of dose escalations necessary.

For the phase II portion of the study, 32 patients will be accrued. The primary endpoint of this portion is disease response (CR+ PR+ SD) at 4 months.

Patients will be accrued to the protocol according to a two-stage Minimax design. Based on patient disease control at 4 months (CR + PR + SD), we will either conclude that the therapy is effective or ineffective. The two-stage design has the smallest maximum sample size with the following two properties:

- (1) if the true disease control rate is less than or equal to 5%, we will conclude that the therapy is ineffective with probability of at least 0.90 ( $\alpha = 0.10$ ), and
- (2) if the true disease control rate is at least 20%, we will conclude that the therapy is effective with probability at least 0.90 ( $\beta = 0.10$ ).

At least 1 of 18 patients must have disease control at 4 months in the first stage to proceed to the second stage. If the protocol proceeds to the second stage, at least 4 of 32 patients overall must have disease control at 4 months for the therapy to be considered effective. Six patients treated at the MTD will be counted for disease control in the phase II portion of the study if the treatment plan or the eligibility criteria does not change.

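### Section 8.2 ties no Protocol Monitoring Committee (PMC) safety report to phase II accrual, and the only phase II stopping rule counts disease control

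*Combined protocol and SAP*

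**What the plan says.** **Toxicity counts.** The only rule that counts toxic events is the 3+3 rule: two or more DLTs in up to six patients make a dose non-tolerated (sections 3, 5.1 and 5.1.3). The evaluable set in 5.1.4 is defined for escalation decisions. Section 5.1.3 asks for six evaluable patients to determine the MTD.

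**Phase II stopping.** Section 9.2 has a two-stage rule on disease control: "At least 1 of 18 patients must have disease control at 4 months in the first stage to proceed to the second stage". At the end, at least 4 of 32 are needed. Six patients treated at the MTD count towards the 32 if the treatment plan and eligibility criteria do not change, which leaves 26 new patients.

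**Scheduled PMC reports (section 8.2).** "Safety and monitoring reports are to be submitted to the PMC after completing each odd numbered dose level", "or more frequently if requested by the PMC". The last dated item is: "A final safety and monitoring report must be submitted to the PMC within three months of defining the maximum tolerated dose (MTD").

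**Standing oversight (section 8.2).** "Adverse events will be evaluated continuously throughout the study". "The principal investigator will monitor the data and toxicities to identify trends and will be responsible for revising the protocol as needed to maintain safety". The PMC "monitors its assigned ongoing research protocols for: adverse event reporting, data and safety monitoring" and "may approve the study for continuation, require revisions, suspend or close a protocol". Section 8.3 sets 24-hour SAE reporting. Sections 5.1.5 and 5.1.6 give hold, reduction and discontinuation rules for the individual patient in phase II.

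**Phase II safety aim.** Section 3 lists further study of safety and tolerability at the recommended dose among the phase II objectives.

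**The concern.** Set side by side, these provisions say who may act on phase II toxicity. They do not say by what point in phase II the committee must have seen the accumulated data. Every dated report hangs on a phase I event. The one phase II look with a patient number attached, at 18, asks about disease control and says nothing about tolerability.

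This matters because six patients say little about the toxicity rate of a combination that section 1.5 calls investigational. A dose that looks acceptable in six could still be poorly tolerated, and 26 to 32 more patients would receive it. If the PMC does not ask for more, following section 8.2 as written leaves most of them outside any scheduled report.

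**Working it through.** **1. The plan's own design reproduces.** With a 5% null rate, a 20% target, 18 patients in stage 1 and 32 in all, the probability of an effective conclusion is the sum over x ≥ 1 of Bin(x; 18, p) × P(Bin(14, p) ≥ 4 − x). This gives 0.072 at 5% (stated bound 0.10) and 0.901 at 20% (stated 0.90). The chance of stopping after stage 1 is (1 − p)^18, which is 0.397 at 5%. Nothing is wrong with the efficacy rule. Toxicity simply does not enter it.

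**2. What six patients establish.** One-sided 95% exact upper limits:
- 0 of 6 DLTs: 1 − 0.05^(1/6) = 0.393.
- 1 of 6 DLTs: the p that solves (1 − p)^6 + 6p(1 − p)^5 = 0.05, which is 0.582.

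The chance that a dose shows at most 1 DLT in six is (1 − q)^6 + 6q(1 − q)^5. No document gives a DLT rate for this combination, so q is assumed: 0.35 at q = 1/3, 0.23 at 40% and 0.11 at 50%.

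**3. How far the last dated report reaches.** The Synopsis expects 42 patients in 12 months, or 42/12 = 3.5 a month, averaged over both phases. Suppose phase II opens as soon as the MTD is defined and the final report uses its full three months.
- New patients enrolled by then: 3 × 3.5 = 10.5, about 10.
- Of these, with 42 days complete: (91.3 − 42)/30.44 × 3.5 = 5.7, about 6.
- Enrolled later: 26 − 10 = 16 of 26, or 32 − 10 = 22 of 32 if nobody carries over.

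The cohorts are numbered 0 and 1, so a literal reading of the odd-numbered rule gives one dose-level report, after cohort 1.

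**4. Where accrual-dated reports would fall.** In 42 days about 42/30.44 × 3.5 = 4.8 more patients enrol, say 5. When 12 have matured, about 17 are enrolled; at 18, about 23; at 24, about 29. So reports at 12 and 18 come before accrual of 26 ends, and one at 24 is useful only if all 32 are new.

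**5. An example count, should the sponsor want one.** New patients only, with a hold if 5 of 12, 7 of 18 or 9 of 24 have a DLT-type event. Exact probability of reaching the boundary at some look:

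| Assumed true rate | Looks at 12, 18, 24 | Looks at 12, 18 only |
|---|---|---|
| 20% | 0.10 | 0.09 |
| 33% | 0.53 | 0.47 |
| 40% | 0.76 | 0.69 |
| 50% | 0.95 | 0.91 |

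A lower boundary (4/12, 6/18, 8/24) gives 0.25, 0.73, 0.89 and 0.98 with three looks. It catches more at high rates, at the price of a review in a quarter of trials if the true rate is 20%.

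**The case against.** The strongest reply is that no sentence in the plan is wrong and none promises a phase II toxicity boundary. The dose must first clear the 3+3, and phase II opens only on an adequate safety profile (section 3). After that, section 8.2 has adverse events reviewed throughout, makes the principal investigator responsible for acting on trends, and lets the PMC demand reports, suspend or close. SAEs are reported within 24 hours, and each patient has dose rules. The PMC may also review ongoing studies on a routine cycle. Section 8.2.1 points to an institutional policy that the documents do not reproduce, so that frequency is unknown.

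All of this stands, and it limits the point. Three stronger inferences fail:
- **That phase II runs without safety oversight, or that safety waits for the end-of-study tables.** Section 8.2 says otherwise. Section 9.7 is descriptive, but it does summarise adverse events for the expansion arm.
- **That a boundary would spare a definite number of patients.** Any such figure assumes that the principal investigator and PMC would not act on, say, 5 events in 12 patients. It would be an upper limit only, so none is given here.
- **That the futility rule protects nobody because accrual could run on during the 4-month readout.** Section 9.2 makes stage 2 conditional on the stage 1 result.

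What the reply does not supply is a PMC report tied to phase II accrual. The power to request one is not a date for one.

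**Conclusion.** The point holds in a narrow form and is a cheap improvement, not an error. As written, the scheduled PMC reports end around the start of phase II, and the only phase II stopping rule is about disease control. The phase I evidence leaves DLT rates up to 39% or 58% compatible with passing. On the stated accrual, about 16 of 26 new patients (22 of 32) come after the last dated report.

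The upper limits are exact. The accrual figures assume a steady 3.5 patients a month and phase II opening at once. The true toxicity rates are assumptions. Whether the committee would in practice review the study more often cannot be settled from the documents.

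**What to change.** In section 8.2, require a PMC safety report when 12 and 18 new phase II patients have completed 42 days of treatment, and also at 24 if all 32 are newly enrolled. Each report should give the number of patients with an event that meets the section 5.1.2 definition, and should state how that definition was applied. It opens with any Grade 3 or higher related toxicity and then lists items with duration limits. The cost is two or three extra reports, built from adverse event data already collected and using powers the PMC already has. Without a boundary there are no false alarms. The 1-of-18 and 4-of-32 rules do not change.

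Optionally, add a count that holds accrual for PMC review, such as 5/12, 7/18, 9/24. The price is roughly a 10% chance of an unneeded review at a true 20% rate, plus either about 5 further patients enrolled or a pause of up to 42 days while each look matures. If the sponsor adopts one, it should say whether the six carried-over patients count. Including them, given at most 1 DLT among the six, lowers the three-look probabilities at 20%, 33%, 40% and 50% to 0.03, 0.25, 0.46 and 0.77.

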### 9.3 Analysis Sets

All subjects who receive at least one dose of the study medication will be included in the safety evaluation.

All subjects who undergo at least one staging reassessment will be used for efficacy evaluations.

## 9.4 Statistical and analytical plans

### 9.4.1 Demographic and other baseline characteristics

Demographics and baseline characteristics will be summarized by cohort and by treatment. Quantitative data will be summarized by descriptive statistics. Frequency tables will be provided for qualitative data.

### 9.4.2 Adverse Events

Individual listings of AEs will be provided. The incidence of treatment-emergent AEs and drug-related AEs, respectively, will be summarized by cohort by treatment by worst NCI CTC grade.

## 9.5 Calculation or derivation of safety variables

Safety and tolerability will be assessed in terms of AEs, laboratory data, and vital signs. These will be collected for all subjects. Appropriate summaries of these data will be presented as described in Section 9.8. All subjects who received at least 1 dose of pembrolizumab or ibrutinib will be eligible.

## 9.6 Calculation or derivation of tumor response variables

At each visit subjects will be programmatically assigned a RECIST and irRC visit response of CR, PR, SD or PD depending on the status of their disease compared to baseline and previous assessments. See Appendix B.

## 9.7 Methods of Statistical Analysis

The statistical analyses will be performed by the Biostatistics Group at Moffitt Cancer Center. Data from the dose escalation phase (phase I) and the dose expansion phase (phase II) will be presented separately.

### **Demographic data**

Characteristics of the subjects, including medical history and disease characteristics at baseline will be listed for each subject and summarized by dose group and expansion phase arm. A medical history will be obtained by the investigator or qualified designee. Medical history will include all active conditions, and any condition diagnosed within the prior 10 years that are considered to be clinically significant by the Investigator.

Reasons for discontinuation of investigational product will be listed including the study day of treatment discontinuation and will be summarized by dose group and expansion phase arm.

### **Exposure**

Exposure to investigational product (i.e., total amount of study drug received) will be listed for all subjects.

Total exposure and total time on study (date of last dose minus date of first dose) will be summarized with descriptive statistics. In addition, the number and percentage of subjects with at least one dose interruption/dose delay and at least one dose reduction will be presented separately for the initial period of evaluability defined as 28 days and for any time following this

initial period of the study.

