### **Escalation phase (Phase I)**

The objective of this phase is to investigate the safety, tolerability and recommend the dose of the combination. Ibrutinib and pembrolizumab will be concurrently administered in sequential cohorts of 3- 6 subjects with each receiving pembrolizumab 200 mg every 3 weeks (Q3W) and ibrutinib at doses of 420 mg daily ( cohort 0) and 560 mg daily (cohort 1) .

The first cohort will enroll a minimum of 3 subjects, according to a standard 3+3 design. If 0 out of the first 3 subjects in the first cohort experience a dose-limiting toxicity (DLT), then dose escalation will continue as planned. If 1 out of the first 3 subjects experience a DLT, then the cohort will be expanded to a total of 6 subjects, and if no more than 1 out of 6 subjects experiences a DLT in a given dose cohort, dose escalation will continue as planned. If  $\geq 2$  DLTs are observed in the first dose cohort, the principle investigator will discuss with Janssen on how to proceed. The DLT evaluation period will be defined as the time from the first dose of pembrolizumab and ibrutinib to 42 days after the first dose or if a subject experiences a DLT within this time period. A maximum of 2 cohorts is expected, making a total of approximately 12 evaluable subjects during the dose escalation phase.

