### Treatment

Treatment will be administered on an outpatient basis. For ibrutinib a self-report pill diary will be utilized to report medication adherence. Reported AEs and potential risks are described in Section 8. Dose delays for ibrutinib and pembrolizumab are described in Section 5.1.6. No investigational or commercial agents or therapies other than those described below may be administered with the intent to treat the patient's malignancy. The starting dose of ibrutinib will be 420 mg daily, taken orally. The dose of pembrolizumab is fixed at 200 mg IV over 30 minutes every 3 weeks. Each cycle will last for 3 weeks.

Subjects will be enrolled in 3 + 3 design with 3-6 subjects per cohort to ensure a minimum of 3 and a maximum of 6 evaluable subjects per cohort. It is estimated that two cohorts will be needed during the dose escalation phase of the study as follows:

Dose Escalation Schedule		
Cohort	Dose	
	Ibrutinib	Pembrolizumab
0	420 mg PO qdaily	200 mg IV over 60 min q3wk
1	560 mg PO qdaily	200 mg IV over 60 min q3wk

Based on current available data, the ibrutinib starting dose will be 420 mg (Cohort 0). Ibrutinib dose could be escalated to 560 mg (Cohort +1) based on the safety and tolerability profile of the combination in Cohort 0. If DLT is seen with Cohort 0, the principal investigator will re-evaluate and discuss with Janssen and Merck on how to proceed.

Each subject will receive ibrutinib daily and pembrolizumab Q3W continuously and will undergo assessments for safety (DLTs, AEs, vital signs, clinical laboratory tests, ECOG performance status, and physical examinations) according to the schedule of assessments.

The DLT evaluation period will be defined as the time from the first dose of ibrutinib or pembrolizumab to 42 days (2 cycles) after the first dose or if a subject experiences a DLT within this time period. The total duration of dose interruptions for ibrutinib will be up to 6 days (intermittent or continuously), during a period of 42 days without a subject being deemed

inevaluable.

Rules for dose escalation and de-escalation are as follows:

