### 5.1.2 Definition of dose-limiting toxicity

A DLT is defined as any toxicity not attributable to the disease or disease-related processes under investigation, which occurs from the start of combination ( post dose Day 1 Cycle 1) up to 42 days and is considered by the Investigator to be definitely, probably, or possibly related to the treatment. A DLT will be defined as any Grade 3 or higher treatment-related toxicity that occurs during the DLT evaluation period, including:

1. Any Grade 4 immune-related AE (irAE) irrespective of duration
2. Any Grade 3 or 4 non-infectious pneumonitis irrespective of duration
3. Any Grade 3 irAE, excluding colitis or pneumonitis, that does not downgrade to Grade  $\leq 2$  within 3 days after onset despite maximal supportive care including systemic corticosteroids or downgrade to Grade  $\leq 1$  within 14 days after onset of the event.
4. Any  $\geq$  Grade 2 pneumonitis or interstitial lung disease (ILD) that does not resolve to grade 1 within 3 days of the initiation of maximal supportive care
5. Liver transaminase elevation higher than  $10 \times$  upper limit of normal (ULN) or total bilirubin higher than  $5 \times$  ULN **that lasts for longer than 7 days**. Any grade 3-4 non hematologic toxicity which does not resolve within 4 days will be considered a DLT.

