#### **5.1.4 Definition of evaluable subject**

For decisions on dose escalation, an evaluable subject is defined as a subject that meets all of the following criteria:

- Has received ibrutinib at the protocol-specified dose for at least 36 out of first 42 days of combination therapy
- Has received one infusion of pembrolizumab at the protocol-specified full dose during the first 42 days of therapy
- Has completed the minimum safety evaluation requirement which is defined as the time from consent to 42 days after the first dose.

OR

- Has experienced a DLT any time during the first 42 days of combination therapy.

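### The exposure summary in Section 9.7 sets the evaluability period at 28 days, whereas the DLT and evaluability window is 42 days everywhere else in the plan

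*Combined protocol and SAP*

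**What the plan says.** Section 9.7, under Exposure, states that "the number and percentage of subjects with at least one dose interruption/dose delay and at least one dose reduction will be presented separately" for two periods. The first is "the initial period of evaluability defined as 28 days"; the second is all time after it.

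The sections that define the window give a different length:

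- Section 3 (Escalation phase) runs the DLT evaluation period from the first dose "to 42 days after the first dose or if a subject experiences a DLT within this time period".
- Section 5.1 (Treatment) repeats this as "to 42 days (2 cycles) after the first dose" and states "Each cycle will last for 3 weeks".
- The same section ties evaluability to interruptions over that window: "The total duration of dose interruptions for ibrutinib will be up to 6 days (intermittent or continuously), during a period of 42 days".
- Section 5.1.2 counts DLTs "up to 42 days and is considered by the Investigator to be definitely, probably, or possibly related to the treatment".
- Section 5.1.4 requires of an evaluable subject: "Has received ibrutinib at the protocol-specified dose for at least 36 out of first 42 days of combination therapy". Its other criteria (the pembrolizumab infusion, the minimum safety evaluation, and the alternative route through a DLT) also refer to 42 days.

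**The concern.** Section 9.7 does not offer 28 days as a free reporting cut. It names the evaluability period and gives it a length that contradicts the definition of an evaluable subject. The number is part of an analysis rule, because it decides the column in which a subject's interruption, delay or reduction is tabulated.

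In phase I, Section 5.1.5 bars dose modifications during the DLT period and provides for dosing to be interrupted when toxicity is unacceptable. Interruptions and delays are therefore the main exposure signal of early intolerance. An ibrutinib interruption on day 35 counts towards the 6-day allowance and lies inside the DLT window, yet the exposure table would place it after the evaluability period. A reader of the table would believe that its first column covers the whole window, when it stops two weeks short.

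**Working it through.** **Inputs.** Cycle length 21 days and DLT period of two cycles (Section 5.1, Treatment); at least 36 of 42 dosed days (Section 5.1.4); interruption allowance 6 days (Section 5.1, Treatment); reporting cut 28 days (Section 9.7, Exposure); 3 to 6 subjects per cohort (Section 3); 6 to 12 phase I subjects in total (synopsis).

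**1. The plan's own window.** 2 × 21 = 42 days, as stated. 42 − 36 = 6 days of permitted interruption, also as stated. Sections 3, 5.1, 5.1.2 and 5.1.4 agree with one another.

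**2. Could 28 days be an alternative evaluability period?** 28 / 21 = 1.33 cycles, which is not a cycle boundary. A subject without a DLT needs at least 36 dosed days, and 36 > 28, so nobody could meet that criterion within 28 days. The other uses of 28 days (Sections 6.1, 6.6 and 7.1) are the pre-treatment screening window.

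**3. The interval concerned.** Taking the first dose as day 1, days 29 to 42 are 42 − 28 = 14 days, and 14 / 42 = 33% of the window. This is a share of calendar days, not of subjects or events.

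**4. Who is misplaced.** The count is of subjects with at least one event in each period:

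| Interruptions or delays in the first 42 days | Initial period, cut at 28 | Initial period, cut at 42 |
|---|---|---|
| First on days 1 to 28 only | counted | counted |
| Both before and after day 28 | counted | counted |
| First on days 29 to 42 | **not counted** | counted |

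Only the third row changes.

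**5. Size for one such subject.** In a cohort of 6, 1 / 6 = 17 percentage points; in a cohort of 3, 1 / 3 = 33 points. This assumes that the table is shown by cohort, which the Exposure paragraph does not say. Pooled over 6 to 12 phase I subjects, it would be 1 / 12 = 8 to 1 / 6 = 17 points.

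**6. Illustration (assumption, not from the documents).** Let p be the proportion of subjects with an interruption within 42 days, with a constant hazard. The share of those subjects whose first interruption falls on days 29 to 42 is 1 − [1 − (1 − p)^(28/42)] / p.

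| p | Proportion with first event by day 28 | Share first interrupted on days 29 to 42 |
|---|---|---|
| 10% | 6.8% | 32% |
| 20% | 13.8% | 31% |
| 30% | 21.2% | 30% |
| 50% | 37.0% | 26% |

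The true share could be lower or higher if interruptions cluster early or late.

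**The case against.** The strongest reply is that this is one inconsistent number in a descriptive table on which no decision rests. That stands. Escalation, DLT counting, the MTD, the primary endpoint and the sample size are governed by Sections 5.1, 5.1.2 to 5.1.4 and 9.2, none of which refers to the exposure summary.

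The scope is also narrow. Section 5.1.4 defines this evaluability for dose-escalation decisions, so it concerns the phase I subjects. For phase II, Sections 4.3.1 and 9.3 make evaluability depend on a post-baseline disease assessment, and Section 9.7 presents the two phases separately. For phase II subjects the boundary is only a reporting cut. Because phase I allows no dose modification during the DLT period, its reduction counts should be little affected.

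Three stronger readings are tempting but are not supported:

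- A reader might infer that the 28-day cut prevents a check of the 36-of-42-day rule. The table could not provide that check at 42 days either. It counts subjects with at least one event, so a subject who misses 1 day and one who misses 10 count alike. The check needs each subject's dosing days, for which the protocol has a pill diary.
- A reader might infer that a cycle 2 infusion delayed beyond day 28 is misplaced. That infusion is due on day 22, so it is already late by day 28 and, dated by onset, falls in the initial period under either cut. It would move only if delays were dated by the eventual infusion, and the plan gives no dating rule.
- A reader might infer that one third of early events are misreported. The one third is calendar time, and subjects with an earlier event remain in the first column.

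Finally, it can be argued that the label is wrong rather than the number. The documents do not exclude this, so the correction should allow for it.

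**Conclusion.** The point holds as an internal inconsistency of minor weight. The length that Section 9.7 gives to the evaluability period is contradicted by every section that defines the window, and it cannot be reconciled with the 36-day dosing requirement.

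The consequence is confined to subjects, mainly in phase I, whose first interruption or delay falls on days 29 to 42. They are missing from the initial-period count and appear only in the later one. How many there will be cannot be known from the documents. One subject is enough to change a cohort's percentage visibly, if the table is shown by cohort and the denominator is the 3 to 6 subjects planned; replaced subjects would enlarge the denominator and reduce the shift. The trial's conclusions on dose and efficacy are not at risk from this.

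**What to change.** In Section 9.7 (Exposure), change 28 days to 42 days, so that the reporting period matches Section 5.1.4. If a 28-day cut is intended, for example for phase II, remove the evaluability label, state it as a separate reporting cut with a reason, and keep a 42-day period for the phase I table.

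The cost is an edit of one number, or of one sentence in the second case. It needs no additional data or subjects and alters no treatment rule. It should be made before the exposure tables are programmed.
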